Table 3-8. Analysis Windows for HCV Serology and HCV RNA Assessments for the All B/F/TAF Analysis.....22

Table 3-9. Analysis Windows for Safety ECG the Randomized Phase Analysis.....22

Table 3-10. Analysis Windows for Safety ECG the All B/F/TAF Analysis23

LIST OF ABBREVIATIONS

3TC	lamivudine
ABC	abacavir
AE	adverse event
ALP	alkaline phosphatase
ALT	alanine aminotransferase
ANOVA	analysis of variance
ARV	antiretroviral
ART	antiretroviral treatment
AST	aspartate aminotransferase
BIC	bictegravir
B/F/TAF	fixed dose combination of bictegravir (BIC; B) 50 mg / emtricitabine (FTC; F) 200 mg / tenofovir alafenamide (TAF) 25 mg
BLQ	below limit of quantitation
BMI	body mass index
CDER	Center for Drug Evaluation and Research
CG	Cockcroft-Gault
CI	confidence interval
CMH	Cochran-Mantel-Haenszel
CRF	case report form
CSR	clinical study report
CV	coefficient of variation
DC	premature study drug discontinuation
DNA	deoxyribonucleic acid
DTG	dolutegravir, ticvicy
ECG	electrocardiogram
eCRF	electronic case report form
eGFR	estimated glomerular filtration rate
eGFR _{CG}	estimated glomerular filtration rate using Cockcroft-Gault formula
FDA	Food and Drug Administration
FDC	fixed dose combination
F/TAF	fixed dose combination of emtricitabine (FTC; F)/ tenofovir alafenamide (TAF)
FTC, F	emtricitabine
GEN	Genvoya, E/C/F/TAF
GFR	glomerular filtration rate
Gilead	Gilead Sciences, Inc.
GLPS	Global patient safety
GS-9883	bictegravir
HBcAb	hepatitis B core antibody
HBeAb	hepatitis B e-antibody
HBeAg	hepatitis B e-antigen
HBsAb	hepatitis B surface antibody
HBsAg	hepatitis B surface antigen

HBV	hepatitis B virus
HCV	hepatitis C virus
HCVAb	hepatitis C antibody
HDL	high density lipoprotein
HIV-1	human immunodeficiency virus (Type 1)
HLGT	high level group term
HLT	high level term
ICH	International Conference on Harmonisation of Technical Requirements for Registration of Pharmaceuticals for Human Use
ID	identification
IDMC	independent data monitoring committee
IWRS	interactive web response system
LDL	low density lipoprotein
LLT	lowest level term
MedDRA	Medical Dictionary for Regulatory Activities
MH	Mantel-Haenszel
OL	open label
PEP	post-exposure prophylaxis
PrEP	pre-exposure prophylaxis
PK	pharmacokinetic
PP	per protocol
PT	preferred term
Q	quartile
Q1	first quartile
Q3	third quartile
QD	once daily
RBP	retinol binding protein
RNA	ribonucleic acid
SAE	serious adverse events
SAP	statistical analysis plan
SD	standard deviation
SMQ	Standardised MedDRA Query
SOC	system organ class
TAF	tenofovir alafenamide
TFL	tables, figures, and listings
TFV	tenofovir
TSH	thyroid stimulating hormone; thyrotropin
ULN	upper limit of normal
WHO	World Health Organization

1. INTRODUCTION

This statistical analysis plan (SAP) describes the statistical analysis methods and data presentations to be used in tables, figures, and listings (TFLs) in the final analysis clinical study report (CSR) for Study GS-US-380-1490. Final analysis will be performed when all subjects have completed the study or prematurely discontinued from the study drug. This SAP is based on the study protocol amendment 3 dated 6 May 2019 and the electronic case report form (eCRF). The SAP will be finalized before database finalization. Any changes made after the finalization of the SAP will be documented in the CSR.

1.1. Study Objectives

The primary objective of this study is:

- To evaluate the efficacy of a fixed dose combination (FDC) containing bicitegravir (GS-9883; BIC; B) /emtricitabine (FTC; F) /tenofovir alafenamide (TAF) versus dolutegravir (DTG) + a FDC containing emtricitabine/tenofovir alafenamide (F/TAF) in HIV-1 infected, antiretroviral treatment (ART)-naïve adult subjects as determined by the achievement of HIV-1 ribonucleic acid (RNA) < 50 copies/mL at Week 48.

The secondary objectives of this study are:

- To evaluate the efficacy, safety, and tolerability of the 2 treatment groups through Weeks 48, 96, and 144.
- To evaluate the long-term efficacy and safety of FDC B/F/TAF through OL Weeks 48 and 96.

1.2. Study Design

Design Configuration and Subject Population

GS-US-380-1490 is a randomized, double-blinded, multicenter, active-controlled study to evaluate the safety and efficacy of B/F/TAF FDC versus DTG + F/TAF FDC in HIV-1 infected ART-naïve adult subjects.

Treatment Groups

Subjects who provide written consent and meet all eligibility criteria will be randomized in a 1:1 ratio to one of the following 2 treatment groups:

Treatment Group 1: FDC of bicitegravir 50 mg/ emtricitabine 200 mg/ tenofovir alafenamide 25 mg (B/F/TAF) + Placebo to match dolutegravir 50 mg and Placebo to match FDC of emtricitabine 200 mg/tenofovir alafenamide 25 mg (F/TAF) administered orally, once daily, without regard to food (n=300)

Treatment Group 2: Dolutegravir 50 mg + FDC of emtricitabine 200 mg/tenofovir alafenamide 25 mg (F/TAF) + Placebo to match FDC of bicitegravir 50 mg/ emtricitabine 200 mg/ tenofovir alafenamide 25 mg (B/F/TAF) administered orally, once daily, without regard to food (n=300)

Key Eligibility Criteria

Medically stable HIV-1 infected subjects who meet the following criteria:

- Plasma HIV-1 RNA levels \geq 500 copies/mL at screening
- ART-naive (\leq 10 days of prior therapy with any antiretroviral [ARV] agent following a diagnosis of HIV-1 infection) except the use for pre-exposure prophylaxis (PrEP) or post-exposure prophylaxis (PEP), up to 1 month prior to screening.
- Screening genotype report must show sensitivity to FTC and tenofovir (TFV)
- Estimated GFR \geq 30 mL/min according to the Cockcroft-Gault formula for creatinine clearance

Study Periods / Phases

Subjects will be treated for at least 144 weeks during the blinded treatment phase. After Week 144, all subjects will continue to take their blinded study drug and attend visits every 12 weeks until the End of Blinded Treatment Visit. Once the last subject completes the Week 144 visit and Gilead Sciences Inc. (Gilead) completes the Week 144 analysis, all subjects will return to the clinic (preferably within 30 days) for an End of Blinded Treatment Visit. At the End of Blinded Treatment Visit, subjects will be given the option to receive B/F/TAF FDC in an open-label (OL) extension phase for 96 weeks. After Week 96 OL, subjects will discontinue the study drug, transition onto commercially available treatment and complete a 30-Day Follow-up Visit. In a country where B/F/TAF is not available, subjects will be given the option to continue OL B/F/TAF until the product becomes accessible to subjects through an access program, or until Gilead elects to discontinue the study in that country, whichever occurs first.

All subjects participating in the OL extension phase, without regard to their blinded treatment regimen, will return for study visits at Week 12 OL and every 12 weeks thereafter for 96 weeks.

Subjects who complete the study through the End of Blinded Treatment Visit and do not continue on the OL B/F/TAF FDC extension phase will be required to return to the clinic after the End of Blinded Treatment Visit for a 30-Day Follow-Up Visit.

Treatment assignments will be provided to the investigators within 30 days of the last subject completing the End of Blinded Treatment Visit.

Schedule of Assessments

After screening procedures, eligible subjects will be randomized 1:1 to Treatment Group 1 or Treatment Group 2 and treated for 144 weeks. Following the Day 1 visit, subjects will be required to return for study visits at Weeks 4, 8, and 12, and then every 12 weeks from Week 12 through Week 144. After Week 144, all subjects will continue to take their blinded study drugs and attend study visits every 12 weeks until the End of Blinded Treatment Visit. All subjects participating in the OL extension phase, without regard to their blinded treatment regimen, will return for study visits at Week 12 OL and every 12 weeks thereafter for at least 96 weeks.

For all eligible subjects, blood will be collected at Day 1, Weeks 4, 8, 12, and then every 12 weeks through the End of Blinded Treatment Visit. Blood will also be collected at Week 12 OL and every 12 weeks thereafter for at least 96 weeks during the OL extension phase. Laboratory analyses (hematology, chemistry, and urinalysis), HIV-1 RNA, CD4+ cell count, and complete or symptom-directed physical examinations will be performed at Screening, Day 1, and all subsequent visits.

Adverse events (AEs) and concomitant medications will be assessed at each visit.

More details for study procedures can be found in [Appendix 1](#).

Pharmacokinetics

CCI

For all subjects on study drug, a single anytime pre- or post-dose PK blood sample will be collected at Weeks 8, 24, and 36.

For all subjects on study drug, a trough PK blood sample will be obtained 20-28 hours following the last dose at Weeks 4 and 12. Following an observed dose, one post-dose PK blood sample will be collected between 1 and 4 hours post-dose.

Randomization

Subjects will be randomized in a 1:1 ratio to 1 of 2 Treatment Groups (Treatment Group 1: Treatment Group 2). Randomization will be stratified by HIV-1 RNA level ($\leq 100,000$ copies/mL, $> 100,000$ to $\leq 400,000$ copies/mL, or $> 400,000$ copies/mL) at screening, CD4+ cell count (< 50 cells/ μ L, $50 - 199$ cells/ μ L, or ≥ 200 cells/ μ L) at screening, and region (US or Ex-US) at randomization.

Site and/or Stratum Enrollment Limits

Approximately 150 study sites in North America, Europe, and Latin America participated. There was no enrollment limit for individual sites.

Study Duration

The randomized, double-blind phase of this study is at least 144 weeks in duration. The OL phase is 96 weeks duration.

1.3. Sample Size and Power

A total of approximately 600 HIV-1 infected subjects, randomized in a 1:1 ratio to 2 treatment groups (300 subjects per treatment group), achieves at least 95% power to detect a noninferiority margin of 12% in Week 48 response rate (HIV-1 RNA < 50 copies/mL as determined by the United States [US] Food and Drug Administration [FDA]-defined snapshot algorithm) difference between the 2 treatment groups. For sample size and power computation, it is assumed that both treatment groups have a response rate of 91% (based on Gilead Genvoya [GEN; E/C/F/TAF] Studies GS-US-292-0104 and GS-US-292-0111), that a noninferiority margin is 12%, and that the significance level of the test is at a one-sided 0.025 level. Sample size and power calculations were made using the statistical software package nQuery Advisor (Version 6.0).

2. TYPE OF PLANNED ANALYSIS

2.1. Data Monitoring Committee Analyses

The Week 12 Independent Data Monitoring Committee (IDMC) analysis was conducted after approximately the first 50% of subjects enrolled completed their Week 12 visit or prematurely discontinued the study drug. The Week 24 IDMC analysis was conducted after all subjects enrolled completed their Week 24 visit or prematurely discontinued the study drug. The purpose of these interim analyses was to provide the IDMC with a statistical report for review. More details are documented in the IDMC charter.

Gilead does not have a prior intent to ask the IDMC to review Week 48 results or to consider early termination of the study even if there is early evidence of favorable efficacy for B/F/TAF.

2.2. Interim Analyses

2.2.1. Week 48 Analysis

The Week 48 analysis was conducted after all subjects either completed their Week 48 visit or prematurely discontinued from the study drug.

2.2.2. Week 96 Analysis

The Week 96 analysis was conducted after all subjects either completed their Week 96 visit or prematurely discontinued from the study drug.

2.2.3. Week 144 Analysis

The Week 144 analysis was conducted after all subjects either complete their Week 144 visit or prematurely discontinue from the study drug.

2.2.4. Open Label Week 48 Analysis

The OL Week 48 analysis was conducted after all subjects either complete their open label Week 48 visit or prematurely discontinue from the study drug.

2.3. Final Analysis

The final statistical analysis will be conducted after all subjects either complete the study or prematurely discontinue from the study.

This statistical analysis plan describes the analysis plan for the final analysis.

3. GENERAL CONSIDERATIONS FOR DATA ANALYSES

The Final Analysis will include two sets of analysis: randomized phase analysis and all B/F/TAF analysis. All table summaries in this final analysis will be based on data included in the All B/F/TAF analysis (eg, data collected during the study period when participants were on B/F/TAF). Randomized phase analysis (eg, including data collected during double-blind phase when participants were on the double-blind study drug) and the corresponding analysis window defined in Section 3.8, will be used to support applicable listings where data collected from the double-blind phase are indicated. The wording of randomized phase or double-blind phase might be used interchangeably throughout the SAP and in the TFLs.

Randomized Phase Analysis:

- For subjects who are never treated in the extension phase of the study including those who prematurely discontinue the randomized study drug or who complete the randomized study drug and do not receive any dose of B/F/TAF in the extension phase, all available data will be included in the randomized phase analysis.
- For subjects who complete the randomized phase and receive at least 1 dose of B/F/TAF in the extension phase, the randomized phase analysis will include (1) all available AE, concomitant medication, pregnancy, and death data collected prior to the extension phase first dose date; (2) all available other data, such as laboratory, vital sign, electrocardiogram (ECG), collected on or prior to the extension phase first dose date.

All B/F/TAF Analysis:

- For subjects who receive B/F/TAF in the randomized phase, all available data for subjects who actually receive B/F/TAF in the randomized phase will be included.
- For subjects who actually receive DTG+F/TAF in the randomized phase and receive at least 1 dose of B/F/TAF in the extension phase, (1) all available AE, concomitant medication, pregnancy, and death data with start date **on or after** the first dose date of B/F/TAF in the extension phase and (2) all available other data, such as laboratory, vital sign, and ECG data, collected **after** the first dose date of B/F/TAF in the extension phase will be included. The data collected **on or prior to** the first dose date of B/F/TAF will be used to derive the baseline value for the all B/F/TAF analysis.

Note that all data for subjects who actually receive DTG+F/TAF in the randomized phase and do not receive any dose of B/F/TAF in the extension phase will be excluded from all B/F/TAF analysis. The actual treatment received will differ from the randomized treatment only when the actual treatment received differs from randomized treatment for the entire treatment duration.

Analysis results will be presented using descriptive statistics. For categorical variables, the number and percentage of subjects in each category will be presented; for continuous variables, the number of subjects (n), mean, standard deviation (SD) or standard error (SE), median, first quartile (Q1), third quartile (Q3), minimum, and maximum will be presented.

All statistical tests will be 2-sided and performed at the 5% significance level unless otherwise specified.

For All B/F/TAF analysis, no statistical comparison between treatment groups will be conducted.

By-subject listings will be presented for all subjects in the All Randomized Analysis Set unless otherwise specified, and sorted by subject ID number, visit date, and time (if applicable). Data collected on log forms, such as AEs, will be presented in chronological order within a subject. The treatment group to which subjects were randomized will be used in the listings. Most listings will be provided for all randomized analysis set for data from both phases of the study. Some listings for All B/F/TAF analysis set will also be provided.

In general, age (in years) on the date of the first dose of study drug will be used for analyses and presentation in listings. For randomized but never dosed subjects, age on the date of randomization will be used. For screen failures, age on the date of the informed consent was signed will be used. If only birth year is collected on the eCRF, “01 January” will be used for the unknown birth day and month for the purpose of age calculation, similarly, if only birth year and month are collected on the eCRF, “01” will be used for the unknown birth day for the purpose of age calculation.

In general, permanent discontinuation of the randomized study drug refers to premature discontinuation of the randomized study drug or completion of the randomized study drug. Similarly, permanent discontinuation of the extension phase study drug refers to premature discontinuation of the extension phase study drug or completion of the extension phase study drug. More specifically, for randomized phase analysis, study drug refers to the randomized study drugs (B/F/TAF or DTG+F/TAF); for all B/F/TAF analysis, study drug refers to B/F/TAF.

3.1. Analysis Sets

Analysis Sets define the subjects to be included in an analysis. Analysis Sets and their definitions are provided in this section. Subjects included in each Analysis Set will be determined before the study blind is broken for analysis. The Analysis Set will be included as a subtitle of each table, figure, and listing. A summary of the number and percentage of subjects in each Analysis Set will be provided by treatment group and in total.

3.1.1. All Randomized Analysis Set

The **All Randomized Analysis Set** will include all subjects who are randomized into the two arms of the study. This is the primary analysis set for by-subject listings.

3.1.2. All B/F/TAF Analysis Set

The **All B/F/TAF Analysis Set** will include all subjects who (1) are randomized into the study and (2) have received at least 1 dose of the B/F/TAF in the randomized phase or at least 1 dose of the B/F/TAF in the extension phase. This is the primary analysis set for the all B/F/TAF efficacy and safety analyses.

For efficacy analyses, all efficacy data collected for the all B/F/TAF analysis will be included.

For safety analyses, all safety data collected up to 30 days after permanent discontinuation of the B/F/TAF (including randomized and open label phases) will be included in the safety summaries, unless specified otherwise.

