8.5.1.2. US FDA-defined Snapshot Algorithm

The analysis window at Week 48 is defined as from Study Day 295 to Study Day 378. All HIV-1 RNA data collected on-treatment (ie, including data collected up to 1 day after the last dose date of study drug) will be used in the snapshot algorithm. Virologic outcome will be defined as the following categories:

- **HIV-1 RNA < 50 copies/mL:** this includes subjects who have the last available HIV-1 RNA < 50 copies/mL in the Week 48 analysis window while on randomized treatment
- **HIV-1 RNA ≥ 50 copies/mL:** this includes subjects
 - a) Who have the last available HIV-1 RNA ≥ 50 copies/mL in the Week 48 analysis window while on randomized treatment, or
 - b) Who do not have on-treatment HIV-1 RNA data in the Week 48 analysis window and
 - i) Who discontinue study drug prior to or in the Week 48 analysis window due to lack of efficacy, or
 - ii) Who discontinue study drug prior to or in the Week 48 analysis window due to reasons other than adverse event (AE), death, or lack of efficacy and have the last available HIV-1 RNA up to 1 day after the premature discontinuation of the study drug ≥ 50 copies/mL

- **No Virologic Data in the Week 48 analysis window:** this includes subjects who do not have on-treatment HIV-1 RNA data in the Week 48 analysis window because of the following:
 - a) Discontinuation of study drug prior to or in the Week 48 analysis window due to AE or death (regardless of whether the last available HIV-1 RNA up to 1 day after the premature discontinuation of the study drug < 50 copies/mL or not) or,
 - b) Discontinuation of study drug prior to or in the Week 48 analysis window due to reasons other than AE, death, or lack of efficacy (eg, withdrew consent and loss to follow-up) and the last available HIV-1 RNA up to 1 day after the premature discontinuation of the study drug < 50 copies/mL or,
 - c) Missing data during the window but on study drug.

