3.8.2. Analysis Windows

Subject visits might not occur on protocol-specified days. Therefore, for the purpose of analysis, observations will be assigned to two different sets of analysis windows based on the following tables: the analysis windows for the randomized phase analysis are derived relative the Study Day 1 for the randomized phase analysis, while the analysis windows for the all B/F/TAF analysis are derived relative the Study Day 1 for the all B/F/TAF analysis.

The analysis windows for HIV-1 RNA, CD4+ cell count, CD4 %, hematology, chemistry, urinalysis, urine pregnancy laboratory tests, eGFR_{CG}, vital signs, and weight (if collected) are presented in [Table 3-1](#) and [Table 3-2](#) for the randomized phase analysis and the All B/F/TAF analysis separately.

Table 3-1. Analysis Windows for HIV-1 RNA, CD4+ cell count, CD4 %, HBV DNA, Hematology, Chemistry, Urinalysis, Urine Pregnancy Laboratory Tests, eGFR_{CG}, Vital Signs, and Weight for the Randomized Phase Analysis

Visit ID	Nominal Day	Lower Limit	Upper Limit
Baseline			1
Week 4	28	2	42
Week 8	56	43	70
Week 12	84	71	126
Week 24	168	127	210
Week 36	252	211	294
Week 48	336	295	378
Week 60	420	379	462
Week 72	504	463	546
Week 84	588	547	630
Week 96	672	631	714
Week 108	756	715	798
Week 120	840	799	882
Week 132	924	883	966
Week 144	1008	967	1050
Week K (K is every 12 weeks after previous visit)	K*7	(K-6)*7+1	(K+6)*7

Table 3-2. Analysis Windows for HIV-1 RNA, CD4+ cell count, CD4 %, HBV DNA, Hematology, Chemistry, Urinalysis, and Urine Pregnancy Laboratory Tests, eGFR_{CG}, Vital Signs, and Weight for the All B/F/TAF Analysis

Visit ID	B/F/TAF Group			DTG/F/TAF to B/F/TAF		
	Nominal Day	Lower Limit	Upper Limit	Nominal Day	Lower Limit	Upper Limit
Baseline			1			1
Week 4	28	2	42	NA	NA	NA
Week 8	56	43	70	NA	NA	NA
Week 12	84	71	126	84	2	126
Week 24	168	127	210	168	127	210
Week 36	252	211	294	252	211	294
Week 48	336	295	378	336	295	378
Week 60	420	379	462	420	379	462
Week 72	504	463	546	504	463	546
Week 84	588	547	630	588	547	630
Week 96	672	631	714	672	631	714
Week k	K*7	(K-6)*7+1	(K+6)*7	K*7	(K-6)*7+1	(K+6)*7

NA = Not applicable

Note: For the B/F/TAF group, Study Day 1 is the first dose date of the B/F/TAF received in the randomized phase;

Note: For the DTG/F/TAF to B/F/TAF group, Study Day 1 is the first dose date of the B/F/TAF received in the extension phase.

Note: Week k is every 12 weeks after previous visit.

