Week 48	336	253	504	336	2	504
Week 96	672	505	840	672	505	840
Week k	K*7	(K-24)*7+1	(K+24)*7	K*7	(K-24)*7+1	(K+24)*7

Note: For the B/F/TAF group, Study Day 1 is the first dose date of the B/F/TAF received in the randomized phase;
 Note: For the DTG/F/TAF to B/F/TAF group, Study Day 1 is the first dose date of the B/F/TAF received in the extension phase.
 Note: Week k is every 48 weeks after previous visit.
 NA=Not Applicable.

3.8.3. Selection of Data in the Event of Multiple Records in an Analysis Window

Depending on the statistical analysis method, single values are required for each analysis window. For example, change from baseline by visit usually requires a single value, whereas a time to event analysis would not require one value per analysis window. When a single value is needed, the following rule(s) will be used.

If multiple nonmissing numeric observations exist in a window, then records will be chosen as follows:

- For baseline, the latest available record on or prior to the first dose date of study drug will be selected. If there are multiple records with the same time or no time recorded on the same day, average will be used for the baseline value, except for HIV-1 RNA (see below).
- For postbaseline visits:
 - For CD4+ cell count, CD4%, and HBV DNA, the record(s) collected on the latest day in the window will be selected for analysis.
 - For other numeric observations (ie, except HIV-1 RNA, CD4+ cell count, CD4%, and HBV DNA), the record(s) collected on the day closest to the nominal day for that visit will be selected. If there are 2 days equidistant from the nominal day, the later day will be selected.
 - For any numeric observations except HIV-1 RNA, if there are multiple records on the selected day, the average will be taken.
- For baseline and postbaseline HIV-1 RNA, the latest (considering both date and time) record(s) in the window will be selected. If both “HIV RNA Taqman 2.0” and “HIV RNA Repeat” (ie, the HIV-1 RNA result obtained from an additional aliquot of the original sample) are available with the same collection time, the results from the “HIV RNA Repeat” will be selected for analysis purposes; otherwise, if there are multiple “HIV RNA Taqman 2.0” records with the same collection time, the geometric mean will be taken for analysis purposes.

If multiple valid nonmissing categorical observations exist in a window, records will be chosen as follows:

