6.3.2. Analysis of the Efficacy Endpoints for All B/F/TAF Analysis

6.3.2.1. Analysis of the Proportion of Subjects with HIV-1 RNA < 50 copies/mL by and Missing = Excluded and Missing = Failure Approaches

The proportion of subjects with HIV-1 RNA < 50 copies/mL will be analyzed using M = E for imputing missing HIV-1 RNA values using the All B/F/TAF Analysis Set for the all B/F/TAF analysis.

- Missing = Excluded (M = E)

In this approach, all missing data will be excluded in the computation of the percentages (ie, missing data points will be excluded from both the numerator and denominator in the computation). The denominator for percentages at a visit is the number of subjects in the all B/F/TAF analysis set with nonmissing HIV-1 RNA value at that visit.

- Missing = Failure (M = F)

In this approach, all missing data will be treated as HIV-1 RNA \geq 50 copies/mL. The denominator for percentages is the number of subjects in all B/F/TAF analysis set.

For M = E and M=F analyses, the number and percentage of subjects with HIV-1 RNA in the following categories will be summarized:

- < 50 copies/mL
 - < 20 copies/mL
 - < 20 copies/mL Not Detectable
 - < 20 copies/mL Detectable
 - 20 to < 50 copies/mL

- 50 to < 200 copies/mL
- 200 to < 400 copies/mL
- 400 to < 1000 copies/mL
- ≥ 1000 copies/mL
- Missing (only applicable for M=F analysis)

For all B/F/TAF analyses, the 95% CI for the proportion of subjects with HIV-1 RNA < 50 copies/mL for a treatment group will be constructed using the Clopper-Pearson exact method.

For M =F analysis, results will be summarized by visit up to Week 240 for B/F/TAF group and up to Week 96 for DTG + F/TAF to B/F/TAF group. For the M = E analysis, results will be summarized by treatment group for all visits through the end of study. No statistical comparison will be made for the all B/F/TAF analysis.

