6.3.2.2. Analysis of CD4+ Cell Count and CD4%

The analysis of CD4 cell count will be based on on-treatment data (ie, up to 1 day after the last dose date of study drug) using the all B/F/TAF Analysis Set for the all B/F/TAF analysis.

The changes from baseline in CD4+ cell count at each visit will be summarized by treatment group using descriptive statistics. No statistical comparisons will be made for the all B/F/TAF analysis.

Similar analysis will be conducted for CD4% using the all B/F/TAF Analysis Set for the all B/F/TAF analysis.

In addition, the mean and 95% CI of change from baseline in CD4+ cell count over time while receiving B/F/TAF will be plotted.

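### The M=E and M=F analyses set no on-treatment limit for HIV-1 RNA, so Week 96 OL in the DTG-to-B/F/TAF group is taken from the follow-up sample after study drug

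*SAP*

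**What the plan says.** **Data scope.** SAP Section 3 first describes the All B/F/TAF analysis by example: "eg, data collected during the study period when participants were on B/F/TAF". Its bullets are wider. For the B/F/TAF group, "all available data for subjects who actually receive B/F/TAF in the randomized phase will be included". For patients switched from DTG + F/TAF, all laboratory data after the first OL dose are included, with no end point. SAP 3.1.2 repeats the open scope for efficacy ("For efficacy analyses, all efficacy data collected for the all B/F/TAF analysis will be included") but limits safety data to 30 days after permanent discontinuation.

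**HIV-1 RNA analysis.** SAP 6.3.2.1 defines M=E by whether a value is present at the visit and M=F by whether it is missing. Neither definition mentions last dose. M=F is tabulated "up to Week 240 for B/F/TAF group and up to Week 96 for DTG + F/TAF to B/F/TAF group"; M=E runs to the end of the study. Protocol 8.5.3 adds no limit.

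**CD4 analysis.** SAP 6.3.2.2 states that the analysis of "CD4 cell count will be based on on-treatment data (ie, up to 1 day after the last dose date of study drug"). Protocol 8.5.1.2 puts the same limit on HIV-1 RNA, but only for the snapshot algorithm.

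**Windows and selection.** SAP Table 3-2 sets Week 96 at Day 631-714. "For the DTG/F/TAF to B/F/TAF group, Study Day 1 is the first dose date of the B/F/TAF received in the extension phase". SAP 3.8.3 adds: "For baseline and postbaseline HIV-1 RNA, the latest (considering both date and time) record(s) in the window will be selected".

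**Visits after study drug.** Protocol 3.4 has patients stop study drug after Week 96 OL, move to commercial treatment and attend a 30-Day Follow-up Visit. Protocol 6.6.2 times that visit at 30 ± 6 days after completing study drug and includes plasma HIV-1 RNA. Protocol 6.5.2 and 6.6.1 ask patients who stop blinded drug to keep attending visits until the End of Blinded Treatment Visit.

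**The concern.** Each rule is ordinary alone. Together, an open data scope, an 84-day window and a latest-record rule let an off-drug sample displace the on-drug sample that the visit is meant to represent. At Week 96 OL this would happen to nearly every DTG-to-B/F/TAF patient who finishes on schedule and attends follow-up. CD4 for the same visit would come from the on-drug period and HIV-1 RNA from about a month later.

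M=F is weakened too. It should count a patient with no on-drug value as a failure, but a follow-up or post-discontinuation sample makes the value non-missing and possibly a success.

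SAP 6.2.1 sends the Week 96 OL endpoint to Section 6.3 of this SAP, so the gap bears directly on an analysis still to be run.

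**Working it through.** **1. Reproduce the window.** The general formula in Table 3-2 is (K−6)×7+1 to (K+6)×7. For K = 96: 90×7+1 = 631 and 102×7 = 714. This matches the table.

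**2. Study day of the Week 96 OL visit.** OL visits are counted from the End of Blinded Treatment Visit (Protocol 6.5.3), and study day = date − Day 1 + 1 (SAP 3.8.1). Ninety-six weeks is 672 days. The visit is nominally Day 673 if the first OL dose is taken on the End of Blinded Treatment Visit day, or Day 672 if it is taken the day after. The visit tolerance is ±6 days.

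**3. Study day of the follow-up sample.** Follow-up day = visit day + visit deviation (−6 to +6) + 30 + follow-up deviation (−6 to +6), giving 13 × 13 = 169 combinations. A last dose on the day before the visit shifts everything by −1.

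| Nominal visit | Last dose | Follow-up range | Inside Day 631-714 |
|---|---|---|---|
| Day 672 | visit day | 690-714 | 169 of 169 |
| Day 672 | day before | 689-713 | 169 of 169 |
| Day 673 | visit day | 691-715 | 168 of 169 |
| Day 673 | day before | 690-714 | 169 of 169 |

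**4. Apply the latest-record rule.** The follow-up sample is later than the Week 96 OL sample and in the same window, so it is selected. It lies 30 ± 6 = 24-36 days after the last dose. Under the CD4 rule the last eligible day would be Day 666-680 across these cases. The follow-up sample is at least 24 − 1 = 23 days past that limit.

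**5. Early stoppers, DTG-to-B/F/TAF group.** Suppose OL drug stops on Day X. The discontinuation visit is X+0 to X+3 (within 72 hours), and follow-up comes 30 ± 6 days after it, so on X+24 to X+39. For X = 607-630, before the window opens, this runs from 607+24 = 631 to 630+39 = 669. Every permitted combination lies inside the Week 96 window. With nominal timing and no delay, X = 601-630. If the patient attends follow-up, M=F does not count the visit as missing.

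**6. B/F/TAF group.**
- *Blinded-phase visits.* HIV-1 RNA from patients who stopped B/F/TAF and kept attending is non-missing and enters both analyses. At the planned 300 per group, each such patient below 50 copies/mL adds 1/300 = 0.33 percentage points under M=F. The documents give no discontinuation rate, so no total is claimed. OL visits are not affected in this way, because these patients cannot enter the extension.
- *Last M=F visit.* The Week 240 window is 234×7+1 = 1639 to 246×7 = 1722. If the End of Blinded Treatment Visit is on Day D, nominal follow-up is D + 672 + 30, which is at or before Day 1722 only if D ≤ 1020. Week 144 is nominally Day 1008, and the End of Blinded Treatment Visit also waits for the last patient's Week 144 visit and the Week 144 analysis. Week 240 is probably little affected.

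**The case against.** **The text can be read the other way.** SAP 3.1.2 defers to the All B/F/TAF analysis, and the Section 3 parenthesis describes data collected on B/F/TAF. On that reading no off-drug sample enters. But the parenthesis is an example with no stated lag. It cannot be strict, because it covers all tables and the safety tables run to 30 days after drug. If it already limited efficacy data, the explicit CD4 cut-off would be redundant. SAP 3.8.1 also excludes the 30-day follow-up visit by name when imputing last dose, and the window and selection rules do not. The inconsistency in Section 3 is part of the problem, not a cure.

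**Earlier interim SAPs may contain the limit.** They are not available. SAP 6.2.1 cites them for the analyses already done and sends Week 96 OL to Section 6.3, which imports no cut-off.

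**The affected set is narrower than the group.** This stands. Patients who continue OL drug where the product is unavailable have no follow-up visit near Week 96. The counts also assume a last dose at about the visit: if it falls more than 12 days after a Day 672 visit, nominal follow-up passes Day 714 (672 + 12 + 30 = 714). The protocol's schedule shows drug dispensed at Week 96 OL and the SAP's does not, so this timing is not fully settled.

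**The effect may be small.** This also stands. Patients who must stop are, by implication, where the product is marketed, so their next treatment could be the same combination.

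**Counting values after stopping drug can be a legitimate choice.** For the blinded-phase visits this has some force, since Protocol 8.5.3 sets no on-treatment limit. But the SAP does not state such a choice, and it treats CD4 in the same analysis the opposite way.

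**Conclusion.** The concern holds and should be fixed. As written, the rules take HIV-1 RNA at Week 96 OL from a sample 24-36 days after the last dose. This applies to DTG-to-B/F/TAF patients who stop on schedule, take their last dose at about the Week 96 OL visit and attend follow-up. It occurs in 168 or 169 of the 169 permitted timing combinations, depending on the day-count convention. A smaller set of early OL stoppers, and B/F/TAF patients who stopped during the blinded phase, can also contribute off-drug values that M=F would otherwise count as failures.

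The direction of bias is unknown: a gap in treatment could produce rebound, while effective follow-on treatment could fill a missing value with a suppressed one. Its size cannot be computed from the documents. There is no comparison between groups, and the Week 48 primary result is not touched.

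**What to change.** In SAP 6.3.2.1, state that only HIV-1 RNA collected up to 1 day after the last B/F/TAF dose is used, and that this limit is applied before the latest-record rule in 3.8.3. Treat later values as missing (excluded under M=E, failure under M=F) and list them separately. Reword the Section 3 bullets and 3.1.2 so that the efficacy scope agrees.

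Excluding only the 30-Day Follow-up sample from the Table 3-2 windows would be a weaker alternative. It cures the Week 96 OL problem but leaves the blinded-phase off-drug values in.

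The cost is one sentence, two matching edits and reuse of the on-treatment flag already needed for CD4. Discontinuation-visit samples drawn 2-3 days after the last dose would also drop out, as they already do for CD4. Because the SAP is signed, the change belongs in a SAP revision or, as SAP Section 1 provides for changes after finalization, in the clinical study report.
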